3.2.2 ROADSTER Study

In 2012, Silk Road Medical initiated the ROADSTER study, a multicenter trial of 219 patients to evaluate the safety and effectiveness of the ENROUTE Transcarotid Neuroprotection System (ENROUTE NPS) with all FDA-approved carotid artery stent systems. The ROADSTER study showed a low overall 30-day stroke/death rate of 2.8% and a 30-day stroke rate of 1.4%. It was the lowest reported stroke rate of any multicenter trial of carotid revascularization with independent adjudication. The ROADSTER study supported 510(k) clearance of the ENROUTE NPS in 2015.

The rate of serious arterial dissections (those requiring treatment) in the ROADSTER study was 1.8% (4/219). The rates of arterial dissection deemed to be serious in nature vary across contemporaneous studies of carotid artery stenting and embolic protection devices as shown in Table 1.

Table 1. Rates of Serious Dissection and Hematomas

	ROADSTER	Abbott Acculink (ARChE ^R) P040012¹	Abbott Xact (SECuRITY) P040038	Boston Scientific Wallstent (BEACH) P050019	Covidien Protégé (CREATE) P060001	Cordis Precise (SAPP ^{HIRE}) P030047
Serious Dissection Rate	1.8%	0.0%, 0.72%, 2.07%	3.28%	0.4%	1.2%	Not Reported
Serious Wound/Groin Hematoma	2.3%	Not Reported	Not Reported	2.1%	Not Reported	Not Reported

As these results show, the rate of serious dissection in the ROADSTER study is within the range reported in other pivotal carotid artery stenting and embolic protection device trials (0.0%-3.28%). The rate of serious wound hematoma (defined as non-arterial surgical wound hematomas requiring treatment) was 2.3% (5/219) in the combined population (pivotal and extended enrollment). There were no serious groin hematomas (defined as femoral vein access site hematomas) in the ROADSTER study. Wound/groin hematoma rates are rarely reported in other contemporaneous CAS and EPD studies and thus reports of this event are under-reported in TF-

¹ Rates include ARChE^R 1, 2 and 3 respectively

CAS studies. As a result, direct comparisons against TCAR may not be valid. The BEACH study (Boston Scientific Carotid Wallstent) reported a discreet hematoma rate of 2.1%, and the ROADSTER serious wound hematoma rate is comparable to this rate. The variable definitions and reporting standards for local complications make direct comparisons complex.

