3.2.3 ROADSTER 2 Study

In October 2015, Silk Road Medical initiated the ROADSTER 2 Post-Approval Study, a multicenter study of 692 patients. Results of this study were submitted to FDA on November 25, 2019 via P140026/R013. The primary endpoint was the rate of procedural success at 30 days following the index procedure. Procedural success is defined as acute device success (successful insertion of the ENROUTE NPS and establishment of flow reversal), technical success (deployment of interventional tools) and the absence of a major adverse events (hierarchical stroke/death/myocardial infarction) through 30 days. This study demonstrated a high procedural success rate of 97.9%. High rates of acute device and technical success were demonstrated at 99.7% for both.

The hierarchical major adverse event rate (stroke/death/myocardial infarction) in ROADSTER 2 was 1.7%. The incidence of combined stroke/death was 0.8%. There was one (1) death (0.2%) which was unrelated to both the study device and procedure. That patient expired from a ruptured abdominal aortic aneurysm approximately two weeks following treatment in ROADSTER 2.

There were ten (10) acute cranial nerve injuries reported in the ITT population of ROADSTER 2 (1.4%). Six (6) of ten (10) patients returned for extended follow-up and all cranial nerve injuries had resolved. The resolution of cranial nerve injuries for four (4) patients is unknown, since these patients did not consent to additional follow-up.

There were eight (8) adverse events that were attributed to the study devices (1.3%) including seven (7) arterial dissections (1.1%) and one (1) thrombosed stent (0.2%). The arterial dissection rate in ROADSTER 2 was lower than that of ROADSTER, as ROADSTER 2 used a second-generation device designed to be more atraumatic. In a recent publication comparing TCAR to transfemoral CAS, TCAR was associated with a lower rate of technical failure compared to transfemoral CAS (0.5% vs 1.2%; p<.001)(Schermerhorn et al. 2019).

There were no reports of unanticipated adverse device effects in ROADSTER 2.

TCAR with reverse flow has proven to be a safe and effective treatment for carotid revascularization. With over 20,000 procedures performed worldwide, physician utilization of TCAR has started to evolve into other therapeutic areas for the benefits of the access and the protective aspects of reverse flow.

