11.4 Patient Flow Diagram

[figure not shown]

Image also provided in Appendix 5.

12 Adverse Events

Adverse event (AE) data will be collected and recorded from index procedure through 90-day follow-up period (or until patient discontinuation) for all enrolled patients on the Adverse Event CRF. At each evaluation, the Investigator or coordinator will determine whether an adverse event has occurred based on, but not limited to reports from the study patient, observed by the investigator or coordinator or documented in the medical record. For the purpose of this protocol, an adverse event is any untoward medical occurrence in a study patient, which may or may not have a causal relationship with the study device. It includes any pre-existing condition that increases in severity or frequency or any new events that occur after the index procedure. An elective procedure for a pre-existing condition (that has not worsened) is not considered an AE.

Event, date of onset, duration, severity, seriousness, treatment, outcome and relationship to the device or procedure will be recorded on the Adverse Event CRF and cross-tabulated according to:

- Severity (Mild, Moderate, Severe)
- Seriousness (Serious Adverse Event (SAE), Non-serious AE)
- Serious Adverse Device Effect (SADE)
- Unanticipated Adverse Device Effect (UADE)
- Procedure-Relatedness (Not Related, Possibly Related, Probably Related, Causal/Related)
- Device-Relatedness (Not Related, Possibly Related, Probably Related, Causal/Related)

Anticipated AEs have been listed in Section 23.1, 23.2, 23.3 & 23.4, and all AEs will be monitored until they are adequately resolved or explained at the end of the study follow-up period. Beyond the routine annual reports, interim progress report will be provided every three months to FDA.

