2. INTRODUCTION

The purpose of this Statistical Analysis Plan (SAP) is to prospectively outline the methods for analyses for patients with acute ischemic stroke in the anterior circulation due to large vessel occlusion (LVO) who underwent endovascular treatment using the transcarotid approach with flow reversal in this initial feasibility (NITE 1) study using the NOVIS Neuroprotection System (NPS).

The NITE 1 study is a prospective, multi-center, single arm feasibility study for the endovascular treatment of patients with acute ischemic anterior circulation strokes due to large vessel embolic occlusions using the transcarotid approach with flow reversal. Patients enrolled into the NITE 1 study will have failed transfemoral therapy and will be followed immediately from post-op to 90 days. The primary study objective is to establish the feasibility and safety of the NOVIS NPS in the targeted study population, and as such, this SAP will focus on confirming whether the initial safety signal exists from the primary endpoint data.

With FDA's IDE approval of the study design and sample size, the primary safety study endpoints will be numerically compared to existing TCAR data from the ENROUTE NPS clinical program (PROOF and ROADSTER). The functional independence at 90 days will be compared to reference data for acute ischemic stroke (AIS) patients treated with mechanical thrombectomy and the natural history of AIS in those patients who have not received or have failed mechanical thrombectomy, as cited in Section 5. The primary study endpoints for the NITE 1 study include:

- Device-related Serious Adverse Events – vascular complications including dissection, pseudoaneurysm, hematoma, arteriovenous fistula, thrombus formation, embolization and any vascular complication that may be attributed to the device AND requires surgical repair, surgical wound revision, transfusion, etc.
- Other Serious Adverse Events – permanent cranial nerve injury (CNI), new symptomatic intracranial hemorrhage (SICH) and dissections related to ancillary devices
- Functional independence at 90 days (proportion with mRS score 0-2)

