As listed above, the first data review will compare the incidence of the device-related SAEs from NITE 1 to the device-related SAEs collected across the body of TCAR evidence to date. This comparison group will include device-related SAEs from the ENROUTE NPS clinical program (e.g., PROOF and ROADSTER) representing a patient population spanning from feasibility to pivotal to post-market study settings. In addition, the incidence of permanent CNI and new SICH from the NITE 1 patient population will be compared to the same comparison group as well as reference data for AIS patients treated with mechanical thrombectomy and the natural history of AIS in those patients who have not received or have failed mechanical thrombectomy. The use of ENROUTE NPS clinical program data as a point of comparison for device-related SAEs and permanent CNI is based on the comparability of ENROUTE NPS and NOVIS NPS. Although each device is used for different patient populations, the surgical approach and set-up of each NPS device are equivalent. In regard to new symptomatic hemorrhage, the risk for this event can be attributed to two main causes: the risk due to cerebral reperfusion injury and the risk due to interventional or mechanical manipulation of the cerebral vasculature. The first applies to both ENROUTE NPS and NOVIS NPS, since any carotid revascularization comes with risk for cerebral reperfusion injury. The latter may be considered more specific to the AIS patient population. However, due to the increased risk for bleeding among patients treated with ENROUTE NPS due to required use of DAPT pre-procedure and systemic heparinization during the procedure to achieve an ACT of > 250, which is not applicable in the NOVIS NPS procedure for AIS patients, these risks can be considered to offset one another in each population. Therefore, the occurrence for SICH from ENROUTE NPS procedures can be compared to NOVIS NPS. Next, the incidence of dissections related to ancillary devices will be compared to the dissections related to the ancillary devices used commercially for ENROUTE and captured through post-market surveillance data. These numerical comparisons are summarized below with reference to the outcome, comparison group. Finally, the functional modified Rankin Score (mRS) at 90 days will be compared to the average functional independence score at 90 days (mRS 0-2) from the relevant studies included in the meta-analysis by Mokin M, et al in AIS patients treated with mechanical thrombectomy and the natural history of AIS in those patients who have not received or have failed mechanical thrombectomy. These data comparisons are summarized in Table 1 below:

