8. SAFETY

Safety will be assessed by the Data Safety Monitoring Board and events will be adjudicated for review by the Clinical Events Committee, as outlined in the NITE 1 protocol. For final analysis of the safety events, binary rates will be calculated using a denominator as the number of all subjects in the study regardless of their follow-up time.

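### The SAP sets NITE 1 safety rates counted to day 90 beside ENROUTE program rates whose follow-up windows it neither states nor matches.

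*Protocol*

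**What the plan says.** **NITE 1 side.** Protocol section 12: "Adverse event (AE) data will be collected and recorded from index procedure through 90-day follow-up period". SAP section 8: "binary rates will be calculated using a denominator as the number of all subjects in the study regardless of their follow-up time". Neither SAP section 5 with its Table 1 nor section 8 sets an earlier cut for the safety rates.

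**Comparison.** SAP section 2: "the primary safety study endpoints will be numerically compared to existing TCAR data from the ENROUTE NPS clinical program (PROOF and ROADSTER"). SAP section 5 states that "the first data review will compare the incidence of the device-related SAEs from NITE 1 to the device-related SAEs collected" in the TCAR evidence, a pool described as "representing a patient population spanning from feasibility to pivotal to post-market study settings". Permanent cranial nerve injury (CNI), new symptomatic hemorrhage and ancillary-device dissections are compared in the same numerical way. No window is given for either side of these rows. Functional independence, by contrast, is compared at 90 days on both sides.

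**ENROUTE side.** The protocol states an outcome window in two places. Section 3.2.2: "The ROADSTER study showed a low overall 30-day stroke/death rate of 2.8" percent, with a 30-day stroke rate of 1.4%. Section 3.2.3, on ROADSTER 2: "The primary endpoint was the rate of procedural success at 30 days following the index procedure", with major adverse events also counted through 30 days. The ROADSTER rates for serious dissection (4/219) and serious wound hematoma (5/219) carry no window. PROOF results are not described.

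**Cranial nerve injury.** Protocol Appendix 4 defines permanent injury as unresolved at three months. Section 3.2.3 reports ten acute injuries in ROADSTER 2. Six patients came back for extended follow-up and had recovered. The outcome of the other four is unknown because they did not consent to additional follow-up.

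**The concern.** A cumulative proportion means little without its time window. If an ENROUTE rate stops at day 30 and the NITE 1 rate runs to day 90, events in days 31 to 90 can enter one side only. The SAP offers this side-by-side reading as its way of judging whether NOVIS patients are comparable in safety to TCAR patients. With no test and no margin, the displayed numbers are the safety result. The reader needs to know that they cover the same period, and the SAP does not say so.

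Permanent CNI raises a related problem. It cannot be classified at 30 days, and the extra consent needed in ROADSTER 2 suggests that routine follow-up there ended too early to classify it.

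**Working it through.** **1. What the stated 30-day figure covers.** Protocol section 3.2.2 gives 2.8% for stroke/death, and the later ROADSTER text gives 1.4% for death and 1.4% for stroke. 1.4% + 1.4% = 2.8%, so the figure reproduces.

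It does not fit the 219 patients behind the other rates: 6/219 = 2.7% and 7/219 = 3.2%. Read with the neighbouring 0.7%, 1.4%, 99.3% and 95.7%, it fits a denominator of 141 (4/141 = 2.8%). The 30-day label therefore belongs to a different outcome and, apparently, a different patient set from 4/219 = 1.8% and 5/219 = 2.3%. It cannot simply be transferred to them.

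**2. Windows side by side.**

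| Compared outcome | NITE 1 window | ENROUTE window in the documents |
|---|---|---|
| Device-related SAEs | to day 90 | not stated |
| New symptomatic hemorrhage | to day 90 | not stated (also compared with thrombectomy literature) |
| Ancillary-device dissections | to day 90 | not stated; SAP section 5 text cites post-market surveillance, Table 1 the clinical program |
| Permanent CNI | three months by definition | not stated; 4 of 10 unknown in ROADSTER 2 |
| mRS 0-2 | 90 days | 90 days (literature) |

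**3. How large a mismatch could be.** The documents give no event timing, so this is a range under an assumption. Suppose a ROADSTER rate r is a 30-day rate and a share f of 90-day events falls by day 30. The matching 90-day rate is r/f. Under constant hazard it is 1 − (1 − r)³. Expected events are 30 times the rate.

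| Timing | r = 4/219: 90-day rate | events in 30 | r = 5/219: 90-day rate | events in 30 |
|---|---|---|---|---|
| f = 1 | 1.83% | 0.55 | 2.28% | 0.68 |
| f = 0.9 | 2.03% | 0.61 | 2.54% | 0.76 |
| f = 0.75 | 2.44% | 0.73 | 3.04% | 0.91 |
| f = 0.5 | 3.65% | 1.10 | 4.57% | 1.37 |
| constant hazard | 5.38% | 1.61 | 6.69% | 2.01 |

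The added expectation in 30 patients runs from 0 to 1.61 − 0.55 = 1.06 events for dissection, and from 0 to 2.01 − 0.68 = 1.33 for hematoma.

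**4. Against the precision available.** Exact 95% intervals are 0 to 11.6% for 0/30, 0.1 to 17.2% for 1/30 and 0.8 to 22.1% for 2/30. Sampling error exceeds the window effect over the whole range above.

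**5. Permanent CNI in ROADSTER 2.** Ten acute injuries among 692 patients is 1.4%, as stated. With four unresolved by record, the permanent rate lies between 0/692 = 0% and 4/692 = 0.6%.

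**The case against.** The strongest objection is that no 90-versus-30-day mismatch is shown for any compared endpoint. The 30-day windows attach to stroke/death, stroke, procedural success and major adverse events, none of which the SAP lists for comparison. The rates closest to the compared endpoints carry no window, and PROOF is undescribed. The cranial nerve evidence comes from ROADSTER 2, which the SAP does not name; only its mention of post-market settings hints that the study is included. All of this stands. It limits the point to unstated and unaligned windows.

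A reader might also infer that one event after day 30 reverses the comparison, since 1/30 = 3.3% and 1/40 = 2.5% both exceed 1.8% and 2.3%. That does not follow:

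- An event on day 1 has the same effect, so this is a small-sample feature and not a window effect. It also presumes no earlier event of that type.
- At the ITT maximum of 60, 1/60 = 1.7%, below both figures.
- The first comparison is of device-related SAEs as a group. If the ROADSTER dissections and hematomas were in different patients and all counted, the benchmark would be 9/219 = 4.1%, above 1/30.

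Access-related events may also cluster around the procedure, which would make the effect small. The documents neither support nor exclude this.

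Finally, cutting NITE 1 at day 30 throughout could cause harm. If some ENROUTE rates run longer, the cut would create a mismatch in the device's favour and hide late events. That objection is sound, and the remedy has to allow for it.

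**Conclusion.** The point holds as a gap in the SAP: safety rates accumulated to day 90 are compared with ENROUTE rates with no alignment of windows. A mismatch is likely, because every ENROUTE outcome window the documents state is 30 days and ROADSTER 2 follow-up appears to have ended before injuries could be classified at three months. It is unproven for each compared rate. The stronger reading, that the compared TCAR rates are known to be 30-day rates, is not supported.

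The size is unknown. Under the assumption that the ROADSTER dissection and hematoma rates are 30-day rates, the longer window adds between 0 and about 1.1 to 1.3 expected events in 30 patients, the upper end requiring constant hazard. For device-related SAEs, symptomatic hemorrhage and dissections, a shorter comparator window would work against the device. For permanent CNI, the direction depends on how comparator injuries of unknown outcome are counted.

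No hypothesis, margin or success threshold depends on the comparison, so it affects interpretation and not error rates.

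**What to change.** In SAP section 5 and Table 1:

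1. State the follow-up window of each ENROUTE comparator rate, and name the studies in the pool, including whether ROADSTER 2 is among them. Settle which source supplies the ancillary-device dissection rate.
2. Tabulate NITE 1 device-related SAEs, symptomatic hemorrhage and dissections by onset to day 30 and to day 90, with exact confidence intervals.
3. Compare each ENROUTE rate only with the NITE 1 column of the same window. Flag any comparator rate with another or an unknown window as not window-matched.
4. Always report the 90-day totals, so that late events stay visible.
5. Keep permanent CNI at its three-month definition. State how it was ascertained in the comparator, and show comparator injuries of unknown outcome as a best-case to worst-case range (0 to 4 of the 10 in ROADSTER 2, if included).

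The cost is a few sentences and an extra table column, with some comparator rates flagged as unmatched. No new patient data are needed: protocol section 12 already records onset dates, and the sponsor ran the ROADSTER studies and should be able to state their windows.

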3.2.3 ROADSTER 2 Study

In October 2015, Silk Road Medical initiated the ROADSTER 2 Post-Approval Study, a multicenter study of 692 patients. Results of this study were submitted to FDA on November 25, 2019 via P140026/R013. The primary endpoint was the rate of procedural success at 30 days following the index procedure. Procedural success is defined as acute device success (successful insertion of the ENROUTE NPS and establishment of flow reversal), technical success (deployment of interventional tools) and the absence of a major adverse events (hierarchical stroke/death/myocardial infarction) through 30 days. This study demonstrated a high procedural success rate of 97.9%. High rates of acute device and technical success were demonstrated at 99.7% for both.

The hierarchical major adverse event rate (stroke/death/myocardial infarction) in ROADSTER 2 was 1.7%. The incidence of combined stroke/death was 0.8%. There was one (1) death (0.2%) which was unrelated to both the study device and procedure. That patient expired from a ruptured abdominal aortic aneurysm approximately two weeks following treatment in ROADSTER 2.

There were ten (10) acute cranial nerve injuries reported in the ITT population of ROADSTER 2 (1.4%). Six (6) of ten (10) patients returned for extended follow-up and all cranial nerve injuries had resolved. The resolution of cranial nerve injuries for four (4) patients is unknown, since these patients did not consent to additional follow-up.

There were eight (8) adverse events that were attributed to the study devices (1.3%) including seven (7) arterial dissections (1.1%) and one (1) thrombosed stent (0.2%). The arterial dissection rate in ROADSTER 2 was lower than that of ROADSTER, as ROADSTER 2 used a second-generation device designed to be more atraumatic. In a recent publication comparing TCAR to transfemoral CAS, TCAR was associated with a lower rate of technical failure compared to transfemoral CAS (0.5% vs 1.2%; p<.001)(Schermerhorn et al. 2019).

There were no reports of unanticipated adverse device effects in ROADSTER 2.

TCAR with reverse flow has proven to be a safe and effective treatment for carotid revascularization. With over 20,000 procedures performed worldwide, physician utilization of TCAR has started to evolve into other therapeutic areas for the benefits of the access and the protective aspects of reverse flow.

3.2.4 Procedural Times

The average time from skin incision to cannulation of the common carotid artery (CCA) was 13 minutes in the ROADSTER study population (excluding aborted cases). In ROADSTER 2, mean procedure time was 74.8 minutes (skin incision to skin closure). This is comparable to the mean procedure time for transfemoral CAS of 69 minutes as reported in the CREST study(Vilain et al. 2012). Procedure time was not defined in the CREST study.

3.2.5 Anticoagulation

Several studies have been conducted to evaluate the safety of intraprocedural anticoagulation in the acute ischemic stroke (AIS) patient population. A few representative studies are summarized below, which largely demonstrate no difference in functional outcomes and rates of symptomatic

intracranial hemorrhage (sICH) among patients who receive intraprocedural anticoagulation and those who do not.

The TREVO 2 trial (Winningham et al. 2018) evaluated 173 AIS patients who underwent clot retrieval using the Merci coil retriever and Trevo stent retriever. The mRS at 90-days was independently associated with patients who received a heparin bolus, and the rate of TICI 2b/3 reperfusion and intracranial hemorrhages were similar between those who received and did not receive intraprocedural heparin. Another study (Farook et al. 2016) stratified the use of intraprocedural heparin among 76 AIS patients with MCA M1- or ICA-T occlusion and found significantly lower rates of hemorrhage among the heparin group ($p=0.02$). Finally the MR CLEAN registry, a multi-center prospective registry(Van De Graaf et al. 2019), presented data on 1,488 patients with ICA, ICA-T, MCA-M1, MCA-M2, ACA-A1 or ACA-M2 occlusions demonstrating no significant difference among patients treated with intravenous heparin and those without in functional outcomes (adjusted common odds ratio, 1.17; 95% CI, 0.87–1.56), successful recanalization (adjusted odds ratio, 1.24; 95% CI, 0.89–1.71), sICH (adjusted odds ratio, 1.13; 95% CI, 0.65–1.99), or mortality (adjusted odds ratio, 0.95; 95% CI, 0.66–1.38). However, site level analysis showed sites that used heparin more often, also had better functional outcomes (adjusted common odds ratio, 1.07 per 10% more heparin, 95% CI, 1.01–1.13). On the other hand, a Chinese study (Yang et al. 2019), presented an analysis on 619/917 patients from the ANGEL registry, which showed an increased risk for sICH and embolization and lower functional independence with heparinization (9.3 vs. 5.1%, adjusted $p = 0.02$; 7.1 vs. 3.1%, adjusted $p = 0.04$, respectively), although recanalization rates, total ICH, and long-term mortality did not differ between the heparinized and non-heparinized groups (adjusted $p > 0.05$ for all). In conclusion, the summary of these multiple data sets demonstrates comparable outcomes among patients who do and do not receive intraprocedural anticoagulation across functional outcome, sICH, and mortality.

As a result, the sponsor does not believe patients are at any additional risk based on who has or has not received anti-coagulants during the procedure. With the exception of the required use of the pressurized, heparinized saline bag in section 10.3.3, the use of procedural anticoagulation has been carefully considered and will be left to the discretion of the operator.

4 Investigational Study Plan

